7.1.2.1.2 DAY 1 OF TREATMENT PERIOD 1 (V3)

V3 is the second visit of TP1 and takes place in the morning of the day after V2.

The following schedule will be followed during this ambulatory visit:

- Subjects will undergo the necessary assessments and checks to confirm their eligibility;
- Eligible subjects will be randomised;
- Randomised subjects will undergo the pre-dose assessments;
- Subjects will receive the first dose of one of the study treatments (HFA-152a or HFA-134a, according to their randomisation arm);
- Subjects will undergo the post-dose assessments;
- Subjects will be given the necessary instructions before discharge.

The following procedures and assessments will take place:

- Subject selection: specific inclusion and exclusion criteria will be re-checked (see [Section 4.2](#) and [Section 4.3](#), respectively). Subjects not fulfilling the inclusion criteria or meeting any of the exclusion criteria will be recorded as screening failures;
- Randomisation: subjects will be randomised according to [Section 6.5](#);
- Study restrictions: study restriction criteria and adherence to the wash-out requirements applicable before the spirometry assessment will be checked, according to [Section 4.4](#);
- Concomitant medications: concomitant medications taken by the subject since the previous visit and during V3 will be checked and recorded;
- AE recording: the status of AEs ongoing at V2 will be checked and updated in the eCRF when applicable. Any new AE occurring since the previous visit will be checked and recorded in the eCRF, as well as the related concomitant medications. Any AE occurring during this study visit must also be monitored and recorded in the eCRF;
- Physical examination: a full physical examination will be performed, and any new CS abnormality revealed since the screening visit (V1) will be recorded as an AE;
- 12-lead ECG: a single ECG will be recorded to assess ECG parameters (HR, PR, QRS and QTcF), according to [Section 7.2.4](#). The assessment will be performed before or after the vital signs assessment, in pre-dose: within 1 hour before the intake of the first inhalation of the propellant; and in post-dose: 5 minutes, 15 minutes, 1 hour 45 minutes after the intake of the last inhalation of the propellant;

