7.1.2.2.2 DAY 1 OF TREATMENT PERIOD 2 (V6)

V6 is the second visit of TP2 and will take place in the morning of the day after V5.

The following schedule will be followed during this ambulatory visit:

- Subjects will undergo the pre-dose assessments;
- Subjects will receive the first dose of the other study treatment (HFA-152a or HFA-134a, following a cross-over design [[Figure 1](#)]);
- Subjects will undergo the post-dose assessments;
- Subjects will be given the necessary instructions before discharge.

The following procedures and assessments will take place:

- Study restrictions: study restriction criteria and adherence to the wash-out requirements applicable before the spirometry assessment will be checked, according to [Section 4.4](#);
- Concomitant medications: concomitant medications taken by the subject since the previous visit and during V6 will be checked and recorded;
- AE recording: the status of AEs ongoing at V5 will be checked and updated in the eCRF when applicable. Any new AE occurring since the previous visit will be checked and recorded in the eCRF, as well as the related concomitant medications. Any AE occurring during this study visit must also be monitored and recorded in the eCRF;
- Physical examination: a full physical examination will be performed, and any new CS abnormality revealed since the previous physical examination (performed at V3) will be recorded as an AE;
- 12-lead ECG: a single ECG will be recorded to assess ECG parameters (HR, PR, QRS and QTcF), according to [Section 7.2.4](#). The assessment will be performed before or after the vital signs assessment, in pre-dose: within 1 hour before the intake of the first inhalation of the propellant; and in post-dose: 5 minutes, 15 minutes and 1 hour 45 minutes after the intake of the last inhalation of the propellant;

Clinical Study Code No.: CLI-05993AB6-06

Version No.: 1.0

Date: 16 February 2023

EudraCT number: 2022-003247-97

- Vital signs: SBP, DBP and SpO₂ will be measured according to [Section 7.2.3](#). The assessment will be performed before or after the 12-lead ECG assessment, in pre-dose: within 1 hour before the intake of the first inhalation of the propellant; and in post-dose: 5 minutes, 15 minutes and 1 hour 45 minutes after the intake of the last inhalation of the propellant;
- Body temperature: will be assessed according to [Section 7.2.3](#);

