12.3.5 SAFETY VARIABLES

Adverse Events

All AEs starting on or after the time of first study drug intake will be classified as treatment-emergent adverse events (TEAEs). Any AEs started after the informed consent signature and before the time of first study drug intake will be classified as pre-treatment AEs.

The number of TEAEs and the number and percentage of subjects who experienced at least one TEAE will be presented for each study treatment for all AEs, ADRs, SAEs, non-serious AEs, serious ADRs, severe AEs, AEs leading to study discontinuation, and AEs leading to death. Summaries will be presented overall and by system organ class (SOC) and preferred term (PT) based on the MedDRA dictionary.

All AEs will be listed. Pre-treatment AEs will be listed only.

ECG

At baseline and at each post-dose timepoint, the following statistics will be presented for each study treatment for the ECG parameters (HR, QRS, PR, QTcF):

- Mean absolute value with its 95% CI;
- Mean change from baseline with its 90% CI (for post-dose time-points only).

For QTcF, the following categories will also be analysed for each study treatment, by means of descriptive statistics:

- For male subjects: QTcF interval > 450 ms, > 480 ms and > 500 ms;
- For female subjects: QTcF interval > 470 ms and > 500 ms;

Clinical Study Code No.: CLI-05993AB6-06

Version No.: 1.0

Date: 16 February 2023

EudraCT number: 2022-003247-97

- For both, male and female subjects: change from baseline > 30 ms and > 60 ms.

The analysis will be presented at each post-dose timepoint and at any post-dose timepoint.

Vital Signs

At baseline and each post-dose timepoint, the following statistics will be presented by treatment for the vital signs parameters (SBP, DBP, SpO₂):

- Mean absolute value with its 95% CI;
- Mean change from baseline with its 95% CI (for post-dose time-points only).

Lung function parameters

Descriptive statistics on actual values and change from baseline will be presented for FEV₁ and FVC. Both absolute and relative changes from baseline will be presented.

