##### 3.1.2 *Derivation rules*

Pre-treatment AEs are defined as AEs starting between date of informed consent with 00:00 added as time part and the date(time) of first study treatment administration – 1 minute, extremes included.

Treatment-emergent adverse events (TEAE) are defined as AEs starting on or after first administration of any study treatment.

Adverse drug reactions (ADRs) are defined as TEAEs related to study treatment or with missing relationship.

Based on their start date(time), AEs will be allocated to the phase and period during which they started. Phases and periods are defined in section 5.2.1. In case the AE start date(time) is incomplete or missing and the AE could consequently be allocated to more than one phase or period, a worst-case allocation will be done as detailed below:

- Treatment phase vs. non-treatment phase: AE will be allocated to the treatment phase.
- Multiple treatment periods: AE will be allocated to all treatment periods, except periods for which the available parts of the AE start or stop date(time) provides evidence the AE did not occur during that period.

A fatal AE is defined as an AE with outcome ‘fatal’.

An AE for which the study treatment was discontinued is defined as an AE with action taken ‘drug permanently withdrawn’.

	Statistical Analysis Plan	
CLI-05993AB6-06	Final Analysis	Final 1.0 of 05OCT2023

AE onset and duration will be calculated as follows:

- AE onset day (vs. first administration) =
  - AE start date < date of first administration: AE start date – date of first administration
  - AE start date ≥ date of first administration: AE start date – date of first administration + 1 day
- AE onset day (vs. start of period) = AE start date – analysis period start date + 1 day
- AE duration (rounded as detailed in section 5.3.3) =
  - If start and stop date/time are available:
    - AE end date/time – AE start date/time + 1 minute

Note: If AE duration is less than 1 hour, the duration will be presented in minutes. If the AE duration is 1 hour or more, but less than 1 day, it will be presented in hours. If AE duration is 1 day or more, it will be presented in days.

- If only start and stop dates are available:
  - AE end date – AE start date + 1 day
  - date of last contact – AE start date + 1 day (when the AE start date is fully known but the AE is not resolved at the end of the study); in this case the duration will be presented as “>x days”.

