### **3.1.3 Presentation of results**

Tables will present TEAEs only. Pre-treatment AEs will only be listed.

An overview table will show the number and percentage of subjects with at least one event and the number of events by treatment and overall for the following:

- TEAEs
- Serious TEAEs
- Non-serious TEAEs
- ADRs
- Serious ADRs
- Severe TEAEs
- TEAEs leading to study drug discontinuation
- TEAEs leading to death

Separate summary tables by MedDRA system organ class and preferred term will show the number and percentage of subjects with at least one event and the number of events by treatment and overall for the aforementioned categories. Each AE record in the clinical database is considered as a distinct adverse event and is counted as such. Blank system organ classes and preferred terms, if any, will be shown as ‘Not Available’ in the tables and listings.

All AEs, including pre-treatment events and all coding information will be listed. AEs started on or after the date of the follow-up call/visit will be flagged as ‘Follow-

	Statistical Analysis Plan	
CLI-05993AB6-06	Final Analysis	Final 1.0 of 05OCT2023

up'. COVID-19 related AEs will be flagged. Separate listings will be prepared for the categories presented in the summary tables.

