## 5.2 PHASES, PERIODS AND TIME POINTS

### 5.2.1 *Phases and periods*

Adverse events, medications, and procedures will be allocated to phases and periods. All other analyses will not be allocated to phases and periods. Instead, the visit and time point labels indicated on the subject's electronic case report form (eCRF) will be used to allocate the assessments to the correct treatment. Early termination and follow-up visit assessment will be allocated to the last administered treatment.

Adverse events and medications:

Phase	Period	Start	End
Screening		Date of signing the informed consent form (ICF), with 00:00 added as time part	First administration date(time) in the first available period – 1 minute
Treatment	Period 1	First administration date(time) in period 1	First administration date(time) in the next available period – 1 minute
	Period 2	First administration date(time) in period 2	Date of last contact, with 23:59 added as time part

Per definition, and for each subject, the first phase starts on the date of the earliest available ICF signature, with 00:00 added as time part. The last available phase/period ends on the date of last contact, with 23:59 added as time part.

Procedures:

Phase	Period	Start	End
Screening		Date of signing the informed consent form (ICF)	First administration date in the first available period – 1 day
Treatment	Period 1	First administration date in period 1	First administration date in the next available period – 1 day
	Period 2	First administration date in period 2	Date of last contact

Per definition, and for each subject, the first phase starts on the date of the earliest available ICF signature. The last available phase/period ends on the date of last contact.

All tables and figures will present treatments rather than periods.

	Statistical Analysis Plan	
CLI-05993AB6-06	Final Analysis	Final 1.0 of 05OCT2023

AEs, medications and procedures will be allocated to phases and periods as described in sections 3.1.2 and 4.5.2 respectively.

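### AEs are made treatment-emergent and assigned to a propellant by their start, with no rule for worsening, so an ongoing AE that worsens under a later propellant can be left untabulated or counted only under the earlier one

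*SAP*

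**What the plan says.** Both documents define treatment emergence by start time. Protocol 12.3.5: "All AEs starting on or after the time of first study drug intake will be classified as treatment-emergent adverse events (TEAEs". SAP 3.1.2: "Treatment-emergent adverse events (TEAE) are defined as AEs starting on or after first administration of any study treatment". Neither definition mentions an increase in intensity or seriousness.

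Allocation to a propellant follows the same principle (SAP 3.1.2): "Based on their start date(time), AEs will be allocated to the phase and period during which they started". Under SAP 5.2.1, Period 1 ends at "First administration date(time) in the next available period – 1 minute", so it takes in the wash-out and the baseline tracer day of the second period. There is one exception. If the start is incomplete or missing and more than one treatment period is possible, "AE will be allocated to all treatment periods, except periods for which the available parts of the AE start or stop date(time) provides evidence" against it.

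On recording, the visit instructions separate ongoing from new events. At V3, "the status of AEs ongoing at V2 will be checked and updated in the eCRF when applicable"; at V6, "the status of AEs ongoing at V5 will be checked and updated in the eCRF when applicable". New AEs since the last visit are recorded separately. SAP 3.1.1 lists start, stop, intensity, seriousness, relationship, action taken and outcome for each AE, but no date of worsening.

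On display, SAP 3.1.3 tabulates TEAEs only: "Pre-treatment AEs will only be listed". ADRs are defined as a subset of TEAEs, and the serious, severe, discontinuation and death rows are all TEAE rows. Each AE record counts as one event.

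**The concern.** The secondary objective is the safety and tolerability of each propellant, and the by-treatment TEAE tables are its main display. An adverse effect of a propellant may show as the worsening of something already present, not only as a new event. Every subject inhales a radiotracer on the day before the first dose of each period, so mild airway symptoms ongoing at first dose are plausible.

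Two courses show the problem, each assuming that one record is kept and updated:

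- A mild cough begins after the V2 tracer and becomes severe after the first dose at V3. It keeps its V2 start, remains a pre-treatment AE and enters no table, even if it is judged related.
- A throat irritation begins in Period 1 or wash-out and worsens after the first dose at V6. It is counted under the first propellant only. If the grade was overwritten, the severe grade is shown there too.

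Elsewhere the plan does treat worsening as informative. Protocol 10.4 lists it among the causality considerations, and SAP 3.4.3 flags a QTcF that moves from one abnormal category at baseline to a higher one afterwards. No AE counting rule does the same.

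**Working it through.** The plan gives no figure to reproduce, and no formal sample size calculation was done. The check applies the allocation rule to each possible course and then sizes one affected subject.

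**Inputs.** TEAE definition and allocation by start (SAP 3.1.2, Protocol 12.3.5); period boundaries (SAP 5.2.1); pre-treatment AEs listed only and each record counted as an event (SAP 3.1.3); 20 randomised for at least 18 evaluable (Protocol 12.1). Start date(times) are taken as known.

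**Step 1: where each course is counted.** S is before the first dose; P1 and P2 are Periods 1 and 2, with wash-out inside P1.

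| Starts | Worsens | One updated record | New record at worsening |
|---|---|---|---|
| S | S | listed only | listed only |
| S | P1 | listed only | worsening counted under P1 propellant |
| S | P2 | listed only | worsening counted under P2 propellant |
| P1 | P1 | P1 propellant | P1 propellant |
| P1 | P2 | P1 propellant only | P1 propellant and P2 propellant |
| P2 | P2 | P2 propellant | P2 propellant |

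Three of the six courses depend on how the site records the event: S to P1, S to P2, and P1 to P2. Where start and worsening fall under the same propellant, the right column is used either way.

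**Step 2: size of one affected subject.** The change in one treatment's incidence is 1/n, for a subject with no other TEAE in that column.

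- n = 20: 1/20 = 5.0 percentage points.
- n = 18: 1/18 = 5.6 percentage points.

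**Step 3: effect on the difference between propellants.**

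- Any-TEAE row, P1 to P2 course: the event did start in Period 1, so the first column is right. The second column lacks one subject, and the difference is off by 5 points.
- Severe-TEAE row, same course, grade overwritten: the correct entries are 0/20 (first propellant) and 1/20 (second), a second-minus-first difference of +5 points. The tabulated entries are 1/20 and 0/20, a difference of -5 points. The shift is 5 - (-5) = 10 points.
- Severe-TEAE row, original grade kept: both columns show 0/20, and the difference is off by 5 points.

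**Step 4: how often.** The documents give no rate. If each subject has an assumed probability p that an ongoing AE worsens after a later first dose, the chance of at least one such subject among 20 is 1 - (1 - p)^20:

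| Assumed p | Chance of at least one |
|---|---|
| 1% | 18% |
| 2% | 33% |
| 5% | 64% |
| 10% | 88% |

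These values show only how the answer depends on the assumption.

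**The case against.** The strongest reply is that the documents are silent and do not prescribe the failure. Updating the status of an ongoing AE may mean updating its outcome, and nothing forbids a new record when it worsens. The eCRF completion instructions, which might settle this, are not among the documents. Protocol 10.8 requires clinically significant changes at later visits to be reported as AEs, and the V6 and V7 physical examinations turn new clinically significant abnormalities into AEs. Since each record is counted, a new record dated at the worsening would be allocated correctly under the existing rules. The pool of candidates is also narrowed by excluding current infection and by re-checking physical status before randomisation. All AEs are listed with onset and duration, case review of 20 subjects is feasible, and SAE reporting runs from consent whatever the TEAE status.

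Much of this stands, and it rules out stronger readings that a reader might infer:

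- That worsened events are never re-entered. The documents state no rule either way.
- That worsening under a propellant is never counted against it. It is counted when the event began under that propellant, or when a new record is opened.
- That allocation depends on start time without exception. Incomplete or missing starts follow the worst-case rule.
- That each case moves the difference by 10 points. This needs a row such as severe TEAEs and an overwritten grade.

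The gap remains all the same. The sentence in Protocol 10.8 concerns laboratory findings and other abnormal assessments and does not clearly reach a cough or throat irritation already on file. Without a rule, the same clinical course can be recorded in two ways and reach different columns. A listing does not correct a by-treatment table.

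**Conclusion.** The concern holds as a gap in the AE counting rules. For an AE with a known start, emergence and allocation follow the start, and nothing says that worsening opens a new record. If the site does not open one, worsening under a later propellant is either absent from every table or counted only under the earlier propellant.

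The size is about 5 percentage points in one treatment's incidence per affected subject (5.6 with 18 subjects). It reaches 10 points in the difference only in rows such as severe TEAEs, if the later grade replaces the original. This rests on a single updated record per episode and on an unknown frequency of such episodes. If both propellants worsened events equally often, the balanced sequences would make the error non-directional on average. If one did so more often, the rule would tend to hide it.

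Only the descriptive tables for the secondary objective are touched. The point deserves correction but does not threaten the study's primary conclusion.

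**What to change.** In SAP 3.1.2, define a TEAE as an AE that starts, or worsens in intensity or seriousness, on or after the first administration. Count a worsening under the period in which it occurs, and leave the original event in its own period.

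In Protocol 10.8 and the eCRF instructions, have such a worsening entered as a new AE record with its own start date(time), linked to the original, without overwriting the original grade. Both parts are needed: SAP 3.1.1 lists no date of worsening, so a SAP clause alone could not be applied to a single updated record.

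The table layouts can stay, because records are already counted as separate events. The costs are modest: event counts may rise slightly because one episode can give two records, AE duration is split across those records, and the eCRF may need a link field. Within one period, the number of subjects with at least one TEAE does not rise because of the second record.

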### **3.1.3 Presentation of results**

Tables will present TEAEs only. Pre-treatment AEs will only be listed.

An overview table will show the number and percentage of subjects with at least one event and the number of events by treatment and overall for the following:

- TEAEs
- Serious TEAEs
- Non-serious TEAEs
- ADRs
- Serious ADRs
- Severe TEAEs
- TEAEs leading to study drug discontinuation
- TEAEs leading to death

Separate summary tables by MedDRA system organ class and preferred term will show the number and percentage of subjects with at least one event and the number of events by treatment and overall for the aforementioned categories. Each AE record in the clinical database is considered as a distinct adverse event and is counted as such. Blank system organ classes and preferred terms, if any, will be shown as ‘Not Available’ in the tables and listings.

All AEs, including pre-treatment events and all coding information will be listed. AEs started on or after the date of the follow-up call/visit will be flagged as ‘Follow-

	Statistical Analysis Plan	
CLI-05993AB6-06	Final Analysis	Final 1.0 of 05OCT2023

up'. COVID-19 related AEs will be flagged. Separate listings will be prepared for the categories presented in the summary tables.

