
Study design
	
Multiple-dose, open-label, randomised, controlled, 2-way cross-over study.
  
(BID=Twice daily; D=Day; HFA=Hydrofluoroalkane; pMDI=Pressurised metered dose inhaler; V=Visit)
 
The study design proposed in the figure is just an example of one of the possible sequences.

Study phase
	
Phase I

Objectives
	
Primary objective:
 
 To assess the effect of multiple doses of the HFA-152a propellant and the HFA-134a propellant (when administered not in combination with active compounds) on mucociliary clearance (MCC). 
Secondary objective:
 
 To evaluate the general safety and tolerability of the two different propellants.

Treatment duration
	
Two treatment periods, each including an 8-day treatment administration. The two treatment periods will be separated by a 7- to 14-day wash-out period.

Clinical Study Code No.: CLI-05993AB6-06	Version No.: 1.0	Date: 16 February 2023
EudraCT number: 2022-003247-97		

Test product dose/route/regimen	Placebo formulated with HFA-152a propellant via pMDI: Administration: 5 inhalations twice daily (BID [morning and evening]) for 8 consecutive days, starting from the morning of Day 1 until the morning of Day 8.
Reference product dose/route/regimen	Placebo formulated with HFA-134a propellant via pMDI: Administration: 5 inhalations BID (morning and evening) for 8 consecutive days, starting from the morning of Day 1 until the morning of Day 8.
Number of subjects	20 randomised subjects in order to have at least 18 evaluable subjects.
Study population	Male and female adult healthy volunteers.

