4.5 DISCONTINUATION FROM STUDY

Subjects must be discontinued from the study for any of the following reasons:

- An AE occurs that, in the opinion of the Investigator, makes it unsafe for the subject to continue in the study. In this case, the appropriate measures will be taken;
- The subject is lost to follow-up;
- The subject withdraws consent;
- The subject's safety is affected by a violation of inclusion or exclusion criteria;
- The subject's safety is affected by the use of a non-permitted concomitant medication;
- The subject, in the opinion of the Investigator, is unwilling or unable to adhere to the study requirements (i.e. non-compliance);
- The Sponsor, the regulatory authorities, or the Ethics Committee(s) (EC[s]), for any reason, terminates the entire study or for this particular subject;
- The subject becomes pregnant.

It is understood by all concerned that an excessive rate of discontinuations can render a study uninterpretable; therefore, unnecessary discontinuations of subjects should be avoided.

However, should a subject discontinue the study, all efforts will be made to complete and report the observations as thoroughly as possible.

If a subject withdraws consent and cannot or is unwilling to attend the early termination visit, this visit will not be carried-out and no data will be collected after withdrawal.

If the subject has not withdrawn his/her consent, an early termination visit should be scheduled to perform the following safety assessments, as described in [Table 2](#) and [Section 7.1.3](#):

- Physical examination;

Clinical Study Code No.: CLI-05993AB6-06

Version No.: 1.0

Date: 16 February 2023

EudraCT number: 2022-003247-97

- ECG (HR, QRS, PR and QTcF) and vital signs (DBP, SBP and oxygen saturation levels [SpO₂]);
- Recording of AEs, concomitant medications and study restrictions;
- Safety blood assessments (clinical chemistry, haematology, fasting glucose);
- Urine pregnancy test.

If the early termination visit is performed less than 7 days after the intake of the last dose of study treatment, a follow-up call (or visit, if deemed necessary by the Investigator) will also be performed 7 to 10 days after the last dose of study treatment.

In case of discontinuation from the study, the Investigator must fill-in the “Study Termination” page of the eCRF, reporting the main reason for withdrawal.

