10.5 ACTION TAKEN WITH THE STUDY DRUG DUE TO AN ADVERSE EVENT

- Dose not changed;
- Treatment permanently withdrawn;
- Treatment temporarily interrupted;
- Unknown;
- Not applicable.

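### The SAP replaces the protocol's summary of adverse events leading to study discontinuation with one based on drug withdrawal, and does not declare the change

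*SAP*

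**What the plan says.** Protocol Section 12.3.5 lists the categories for which TEAEs and affected subjects are to be counted for each study treatment, overall and by SOC and PT. The list ends with "AEs leading to study discontinuation, and AEs leading to death". The synopsis gives the same list.

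Protocol Section 4.5 ties discontinuation to staying in the study. One ground is "An AE occurs that, in the opinion of the Investigator, makes it unsafe for the subject to continue in the study". The record is a dedicated Study Termination "page of the eCRF, reporting the main reason for withdrawal".

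SAP Section 3.1.3 has a different category in the overview table and in the SOC/PT tables: "TEAEs leading to study drug discontinuation". Table 14.3.1.8 and Listing 16.2.7.8 follow it. The derivation is in SAP Section 3.1.2: "An AE for which the study treatment was discontinued is defined as an AE with action taken" equal to drug permanently withdrawn. The matching option in Protocol Section 10.5 reads "Treatment permanently withdrawn". The other four options there are dose unchanged, temporary interruption, unknown and not applicable.

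SAP Section 6.1, which lists departures from the protocol's analysis, deals only with the lung regions used for mucociliary clearance and the related displays.

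**The concern.** The two categories draw on different fields. The protocol's category asks whether the event ended participation. The SAP's asks what was done with the drug. They can part company whenever no drug is being taken, and this design has such stretches: "The two treatment periods will be separated by a 7- to 14-day wash-out period", and a follow-up call comes 7 to 10 days after the last intake.

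The secondary objective is general safety and tolerability. In a two-period cross-over, an event that keeps a subject from receiving the second propellant is relevant to the tolerability of the first. The protocol planned to show such events by propellant and by SOC/PT. If the SAP's rule misses one, that display understates the count, and nothing in Section 6.1 warns the reader that the definition has changed.

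**Working it through.** The plan gives no figure on this point, so the check is a comparison of texts, with simple arithmetic for scale only.

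1. **Definition and source.** Protocol category: TEAEs leading to study discontinuation; the reason is recorded on the Study Termination page (Protocol 4.5). SAP category: TEAEs with action taken equal to drug permanently withdrawn (SAP 3.1.2). The SAP rule does not use study termination data, and no SAP adverse event table is built on study discontinuation.

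2. **Where the two can differ.** An event during dosing that ends participation also stops the remaining doses, so the permanent-withdrawal option fits. Two windows are less clear:
   - after the Day 8 dose of Period 1 and through the wash-out: nothing is being inhaled, but a second course is still scheduled;
   - after the last Period 2 dose: nothing is being inhaled and no course remains. This window includes the Day 8 imaging, since the radiotracer is given about 2 hours after that dose and images run to 4 hours after it.

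   Neither document says which action-taken option applies in either window.

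3. **Are these events within the protocol's category?** Yes. SAP 5.2.1 runs Period 1 to one minute before the first dose of the next period, and the last available period to the date of last contact. An event in the first window is therefore a TEAE of the first propellant, and one in the second window a TEAE of the second propellant. If it ends participation, it belongs in the protocol's count.

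4. **Is the change declared?** No. SAP 6.1 is silent on adverse events, and so is SAP 3.1.3 on the difference from the protocol.

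5. **What would still show the event.**
   - Tables 14.3.1.1 and 14.3.1.2, and the seriousness, severity and relatedness tables where they apply: the event, under its propellant.
   - Tables 14.1.1.1 and 14.1.1.2: the reason for discontinuation, by sequence and by treatment, without the event term.
   - Listing 16.2.1.2: the event behind the discontinuation.

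   None of these gives event and subject counts by SOC/PT for events that led to study discontinuation.

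6. **Scale.** Randomised subjects: 20 (Protocol 12.1, SAP 1.3). One missed subject in the row for a propellant is 1/20 = 5.0 percentage points. If only 18 subjects were counted for that propellant, it would be 1/18 = 5.6 points. The propellant's overall TEAE rate does not change.

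**The case against.** The strongest reply is that the two categories nearly coincide here. Protocol 4.5 describes only discontinuation from the study and no route for stopping the drug while staying in follow-up. A subject in wash-out still has a course of treatment ahead, and Protocol 10.4 takes the investigational product to mean both propellants. An investigator who cancels that course because of an event could well record a permanent withdrawal. On this view the SAP wording is loose and the counts would agree.

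This stands in part. It shows that the gap is possible, not certain. It does not close it, since no instruction requires that coding, and after the last Period 2 dose there is no course left to cancel.

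The second reply is that little is hidden, because discontinuation reasons are already tabulated by treatment and the event is listed by name. That also stands, and it makes the point a small one. It does not supply the count by propellant and SOC/PT that the protocol planned.

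The third reply is that an event starting days after dosing says little about a product with no active ingredient, when the mean residence time reported for HFA-152a is about 9 minutes. That bears on how to interpret such an event. It does not justify changing a planned category without saying so.

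**Conclusion.** The point holds as a minor one. A category named in the protocol has been replaced by a differently defined one, without declaration. An event that begins in the wash-out or after the last Period 2 dose and ends participation may go uncounted in it. The most that one such subject could cost is about 5 percentage points in a single row and its SOC/PT breakdown. This assumes 20 subjects counted for the propellant and an action-taken value other than permanent withdrawal. How likely that coding is cannot be estimated from the documents.

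Three stronger readings are tempting and are not supported:

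- *Wash-out events would be coded as not applicable.* That option exists, but nothing in either document assigns it to them.
- *The SAP rule would match no records, because it says drug where the protocol says treatment.* The stored eCRF values are not shown. The terms need reconciling, but a failure is not demonstrated.
- *The length of the wash-out measures the risk.* It is 7/23 = 30% to 14/30 = 47% of the days from first dose to the end of Period 2 (8 + 7 + 8 = 23; 8 + 14 + 8 = 30). As a share of Period 1 as the SAP defines it, it is 7/15 = 47% to 14/22 = 64%. These are shares of calendar days and depend on the denominator chosen. They are not the probability that a discontinuing event starts off drug.

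**What to change.** In SAP 3.1.2, define TEAEs leading to study discontinuation as events linked to a Study Termination page on which the main reason is an adverse event. In SAP 3.1.3 and the 14.3.1 tables, add this category to the overview and give it its own SOC/PT table by treatment. Keep study drug discontinuation as an additional category, and bring its action-taken term into line with Protocol 10.5 and the eCRF.

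The cost is one extra row and one extra table. The data are already collected, and Listing 16.2.1.2 already relies on the link between the event and the discontinuation. If the sponsor prefers to keep only the drug-based category, the change should at least be declared in SAP 6.1, although the planned count would then remain unavailable.
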